SAE	Serious Adverse Event	
SDV	Source Data Verification	
SOP	Standard Operating Procedure	
TMF	Trial Master File	

STUDY OVERVIEW		
Full title	Management of Patients with Chronic Liver Disease (CLD) admitted	
	to Hospital as an Emergency.	
Objectives	 To evaluate the impact of different patterns of service organisation, provision and delivery in the English NHS on patient care and outcomes. To identify processes of care that may be used to address the 	
	existing marked inequalities in health, improve patient experience, engagement with healthcare and survival.	
Type of trial	Mixed methods project: this application and protocol relates to quantitative data linkage work package.	
Trial design and methods	This quantitative component will use linked national datasets in combination with a detailed characterisation of general and specialist liver and critical care service provision and practice to study determinants of received care and clinical outcomes of CLD patients after a first emergency admission (EA), in the study period between 1 April 2009 and 31 March 2022 in the English NHS.	
Health condition(s) or problem(s) studied	Emergency hospital admissions of people with CLD.	
Target sample size	Data on approximately 100K subjects	
Trial duration per	Not applicable.	
participant:		
Main inclusion/exclusion criteria:	All adult patients with CLD with a first emergency hospital admission in the study period from 1 April 2009 to 31 March 2022 according to HES-APC data and classified according to ICD-10 diagnostic codes. Data from people who have chosen the National Data Opt-Out will be excluded from the study cohort.	
Statistical methodology	Multiple methods to be utilised: please see statistics plan in section	
and analysis:	9.	
STUDY TIMELINES	2 vears	
Study Duration/length	2 years	
Expected Start Date	01/09/2022	
End of Study definition and anticipated date	Completion of planned analyses and submission of final report. 01/09/2024	
Key Study milestones	Funding already awarded. REC approval 1/09/2022	
STORAGE of SAMPLES (if applicable)		
Human tissue samples	Not applicable	
Data collected / Storage	Only existing data will be used in this part of the study. All data	
	analysed will be de-identified at source. All storage and analysis of the	
	de-identified dataset will be at the London School of Hygiene and Tropical Medicine (LSHTM).	

NHS Foundation Trust

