1 INTRODUCTION

Liver disease is a serious and increasing health problem in the UK. However, people with liver disease often do not know that they are affected until they need to be admitted to hospital as an emergency. These people are often very ill, and a quarter of them die within two months of coming into hospital. The care they get when they are in hospital, and after being discharged, varies greatly across the country. This variation in care has major effects on how long they survive. Survival of those who live in the most deprived areas is half that of those who live in the most well-off ones. We want to understand how and why the place where people live and the care that is available to them affect the way they are treated and their survival. We also want to see how variation in outpatient care after discharge makes a difference. Through this research we hope to understand what clinical practices have the best results and how we can guarantee that they are delivered across the country.

To do this research, we will gather very detailed information about the arrangements for care given to people with liver disease in each hospital in England and then use the health information routinely recorded when people are treated in these hospitals. Information from different parts of the NHS will be 'linked' together into a single database so we can analyse the complete course of people's illness. Data analysed by the research team will have names and all other identifying information removed. We will analyse data from more than 100,000 people with liver disease who had emergency admissions to NHS hospitals in England over more than a decade.

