2 BACKGROUND AND RATIONALE

The increasing prevalence of liver disease in the UK, the resulting increase in morbidity and mortality, and the regional variation in survival has been extensively reviewed in reports of the Lancet Commission on Liver Disease in the UK and the Atlas of Variation in Risk Factors for Liver Disease in England (1,2). Below we summarise these reports as well as evidence from an extended review of the literature that was carried out to support this application. This review highlighted serious questions about the current provision and delivery of care for patients with CLD, especially in patients who were admitted to hospital as an emergency.

Mortality rates from CLD in the UK have increased 400% since 1970, and in people younger than 65 years have risen almost five-fold (1,2). Most patients die in working age and CLD is now the third biggest cause of premature mortality. In 2018, liver disease was the leading cause of death for those age 35-49 years. However, the prevalence of liver disease and its outcome is not uniform across the UK. Studies in England have shown wide variation: premature mortality varies 7.7-fold and hospital admissions 8.5-fold by Clinical Commissioning Group (CCG). This variation is closely linked to the level of socio-economic deprivation. People with CLD who live in the most deprived areas of England die nearly 10 years earlier and have a mortality rate that is twice as high compared to those who live in the most affluent ones (1,2).

CLD has a wide range of different aetiologies. People with CLD, particularly if it is alcohol-related, often first come to medical attention with an unplanned emergency admission (EA) to hospital when their disease is already advanced. Over a quarter of these patients die within 60 days of their first EA (3,4). Re-admissions are common and associated with a worse prognosis, and nearly 70% of patients who survive a first EA will die within 5 years (3).

Provision of specialist care for people with CLD admitted as emergencies shows wide variation across the UK with major imbalances between service provision and local disease burden (5). A study of CLD patients admitted to hospital between 2004 and 2012 in England and Wales suggested that early input

King's College Hospital MHS

NHS Foundation Trust

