4. Impact of regional, hospital and patient characteristics on critical care use of chronic liver disease patients who had a first emergency admission: We will explore the association between which of the regional characteristics (e.g., network arrangements, prevalence of CLD, use of transplantation), hospital characteristics (e.g., transplant centre status, specialist staffing, ICU capacity, ICU case-mix), and patient characteristics (e.g., type of CLD and comorbidity, age, sex, socioeconomic deprivation) are associated with the proportion of cases admitted to critical care, their clinical condition at critical care admission, the duration of critical care, and the proportion of cases for whom critical care was withdrawn. We will also explore changes in critical care use as a result of the Covid-19 pandemic. Multilevel logistic regression models will be used to estimate adjusted odd ratios that capture the impact of the regional, hospital and patient characteristics and the Covid-19 pandemic on critical care use.

5. Critical care use and clinical outcomes after a first EA in patients with CLD: We will characterise hospitals according to the proportion of patients that are admitted to critical care and whether they were admitted to critical care early or late in order to explore to what extent hospitals with more frequent and earlier critical care admissions of CLD patients after an EA have better short-term outcomes (in-hospital mortality and readmissions, total time spent in hospital and mortality during the year following the EA). The results will be analysed using multilevel logistic regression including the level and timing of critical care use as hospital-level characteristics with adjustment for key patient characteristics, including age, sex, socioeconomic deprivation, and comorbidity.

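### Question 4's adjusted odds ratio for deprivation is the gap left after services are held constant, so it should be paired with the gap before services are entered

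*Protocol*

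**What the plan says.** The Protocol's Study Overview lists two objectives. The second begins "To identify processes of care that may be used to address the" and its target is the "existing marked inequalities in health, improve patient experience, engagement with healthcare and survival". The same overview states that the document covers the quantitative data-linkage component, so the objective is not confined to the qualitative work.

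Section 1 sets out to explain the ways in which "the place where people live and the care that is available to them affect the way they are treated and their survival". Section 2 gives the size of the problem. Of the variation in premature mortality and admissions it says "This variation is closely linked to the level of socio-economic deprivation", and it reports that people with chronic liver disease in the most deprived areas "have a mortality rate that is twice as high compared to those who live in the most affluent ones".

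Section 9 has seven research questions and names deprivation in two of them:

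- **Question 4 (critical care use).** Deprivation is one of the patient characteristics, alongside regional characteristics such as network arrangements and hospital characteristics such as specialist staffing and ICU capacity. Multilevel logistic models will "estimate adjusted odd ratios that capture the impact of the regional, hospital and patient characteristics and the Covid-19 pandemic on critical care use".
- **Question 5 (critical care use and later outcomes).** Hospital-level use and timing of critical care are the exposures, with "adjustment for key patient characteristics, including age, sex, socioeconomic deprivation, and comorbidity".

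**The concern.** Question 4 says its adjusted odds ratios capture impact. For deprivation this is doubtful. Staffing, ICU capacity and network membership are plausible routes by which living in a deprived area leads to less access to critical care; section 2 itself reports that service provision is out of balance with local disease burden. If those service variables sit in the same model as deprivation, the deprivation odds ratio compares deprived and affluent patients who have the same services. That is a legitimate quantity, but it is the residual gap. It leaves out whatever part of the gap arises because services are unevenly placed.

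The risk lies in reporting. A ratio near 1 could be taken as showing no inequality in access when the inequality lies in where the services are. No question in section 9 names a deprivation contrast before services are entered, so the reader would have nothing to set beside it.

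**Working it through.** The Protocol gives no figure to reproduce on this point. The check is a reading of section 9 followed by two illustrations with assumed inputs.

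**Step 1: where deprivation appears in section 9.**

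| Question | Role of deprivation |
|---|---|
| 1 Time trends | Not named |
| 2 Regional variation | Not named; the comparison without and with adjustment concerns regional admission rates |
| 3 Networks | Not named |
| 4 Critical care use | One of several patient characteristics, reported as an adjusted odds ratio |
| 5 Critical care and outcomes | Adjustment variable |
| 6 Transplantation | Not named; the variation examined is between regions |
| 7 Outpatient review | Not named |

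Questions 2 and 6 refer to patient characteristics in general, which may include deprivation. The variation they examine is nevertheless between regions, not between deprivation groups.

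**Step 2: can a real access gap vanish from a mutually adjusted ratio?** All inputs are assumptions:

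- 50% of the most deprived and 80% of the least deprived patients are admitted to hospitals with a given service.
- Critical care admission is 30% with the service and 15% without.
- Within each type of hospital, deprivation has no effect.

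Results:

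- Most deprived: 0.5 × 0.30 + 0.5 × 0.15 = 0.225.
- Least deprived: 0.8 × 0.30 + 0.2 × 0.15 = 0.270.
- Risk difference: 0.225 − 0.270 = −0.045, or 4.5 percentage points fewer.
- Crude odds ratio: (0.225/0.775) / (0.270/0.730) = 0.290/0.370 = 0.78.
- Deprivation odds ratio holding the service constant: 1.00, by construction.
- Service odds ratio in the same model: (0.30/0.70) / (0.15/0.85) = 0.429/0.176 = 2.43.

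The whole gap is absent from the adjusted deprivation ratio. The model still shows that the service matters, but not that deprived patients have less of it.

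**Step 3: can the service-adjusted ratios alone tell the reader how large the gap was?** On the log scale, the change on entering services is 1 − ln(OR with services)/ln(OR without services). Hold the adjusted ratio at an assumed 1.5:

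- OR without services 1.5: 1 − 0.405/0.405 = 0%.
- OR without services 2.0: 1 − 0.405/0.693 = 41.5%.
- OR without services 2.5: 1 − 0.405/0.916 = 55.7%.

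A simulation with n = 100,000, a true adjusted deprivation odds ratio of 1.5 and three strengths of link between deprivation and care gave:

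| OR without care | OR with care | Care OR | Change on log scale |
|---|---|---|---|
| 1.49 | 1.51 | 0.40 | −2% |
| 1.83 | 1.53 | 0.41 | 29% |
| 2.07 | 1.52 | 0.39 | 42% |

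The two adjusted ratios are almost the same in every row, while the gap before adjustment differs widely. The adjusted output cannot distinguish these situations; the contrast without services is also needed. The first row shows a small change even though care and deprivation are unrelated there. Odds ratios can shift on adjustment for reasons other than confounding or mediation, which is why the comparison is better made on the risk scale.

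**The case against.** The case against is substantial, and much of it stands.

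- **Section 9 calls itself an overview.** Model sequence and reporting scale are normally left to a statistical analysis plan, which is not at hand. For questions 6 and 7 the Protocol is merely silent, so no fault can be claimed there. What remains is that question 4 itself says what its odds ratios capture.
- **The joint model is inferred.** The text speaks of models in the plural and does not say what each ratio is adjusted for, so nested models would also fit it. Joint adjustment is the natural reading, but not the only one.
- **Question 5 is sound.** A reader might infer that adjusting for deprivation there is a defect because it removes the inequality. It is not. The exposure is a hospital-level pattern of critical care, deprivation is a plausible confounder, and adjustment is correct.
- **The objective is soft and shared.** It speaks of processes that may be used to address inequality and promises no share of the gap explained. The Social Science study has the same aim, and the quantitative objectives in section 3.1 name neither deprivation nor inequality. This limits the weight of the point. But four purposively chosen sites cannot measure a national gradient, while about 100,000 linked records can.
- **The illustration is constructed.** The inputs are assumed and the 1.00 is built in. It shows what can happen, not what will. The service odds ratio of 2.43 would also be visible to an attentive reader.

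**Conclusion.** The point holds in a narrow form. On the natural reading of question 4, the deprivation odds ratio is a residual after services are held constant, and it should not be presented as the impact of deprivation on critical care use. The Protocol names no companion contrast without services, although its own Study Overview sets an inequalities objective. The possible size is shown only by assumption: a gap of 4.5 percentage points (odds ratio 0.78) can appear as 1.00. The conclusion rests on two assumptions: that question 4 adjusts jointly, and that services lie partly on the path from deprivation to care.

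Two stronger readings are tempting and unsupported. One is that the project can say nothing about inequality. Question 4 does study deprivation as a determinant of critical care use, and questions 2 and 6 study regional variation. The other is that comparing models would show what share of the gap care causes. That needs assumptions, such as no unmeasured confounding of service and outcome, which the Protocol does not set out. This is a cheap improvement.

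**What to change.** In question 4, report the contrast between the most and least deprived (for example by quintile) from two nested models on the same patients:

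- (a) age, sex, type of liver disease and comorbidity;
- (b) the same plus hospital and regional service characteristics.

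Give standardised risk differences from each. State that (a) describes the access gap among patients of like case mix and that (b) describes the residual gap at equal services. Model (a) should not condition on hospital: with many patients per hospital, a hospital random intercept absorbs most of the between-hospital part of the gap. Standard errors can allow for clustering instead.

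Report the same pair descriptively for 1-year mortality with the question 5 variables, and keep question 5's own adjustment for deprivation unchanged. Describe the movement from (a) to (b) as descriptive, not as a causal share explained. Interactions between deprivation and a hospital exposure are optional and exploratory, since precision for hospital-level exposures will be limited.

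The cost is a few extra model fits on variables already planned and a longer results section. No new data are needed.

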10 PATIENT AND PUBLIC INVOLVEMENT (PPI)

Consultation with people with liver disease was undertaken at the very earliest initial planning stages of this project. We first held informal discussion with people hospitalised with CLD at King's College Hospital, and with their next of kin, and following an encouraging response developed an initial research plan.

King's College Hospital MHS

NHS Foundation Trust

Through our research partners, the British Liver Trust, we then conducted an online survey of 57 people with CLD from across the UK to understand their attitudes to the goals and basic research methods under consideration. This sample was representative of the patients with CLD who would be in the proposed study cohort in respect of age, sex and cause of liver disease. More than 80% had required hospitalisation as a consequence of CLD. More than 90% felt it "extremely important" to understand regional variations in outcome of CLD. More than 90% supported the research and felt it to be addressing an important subject, endorsing the approaches proposed to be utilised, including the use of de-identified linked electronic health records. Thirty-three of the respondents volunteered to join an online patient consultation group for the research project.

A face-to face focus group was then conducted with 19 people who had LT for CLD, many of whom had experienced EA at an early stage of their illness. This group also confirmed support for the proposed research and its methodology. They also expressed enthusiasm for continued patient participation in the process of research and their feedback reinforced the importance of adequate notification steps and methods for "opt out" of use of personal data for those who did not wish to contribute. As outlined below, the research plan now incorporates an extended PPI component, specific patient notification steps and processes of opt-out.

A patient representative with lived experience of CLD, emergency admission and liver transplant is now a grant co-applicant and member of the research team, as is a representative of a patient organisation, the British Liver Trust (BLT). As members of the research team they will be involved in all stages of the research cycle including prioritising research questions, advising upon and managing the research process and routes to data opt-out, analysing and interpreting the results of research, with a prominent role in dissemination of findings.

A Patient Advisory Group (PAG) is to be recruited that will include people with liver disease and lived experience of drug and alcohol services and homelessness. The PAG will be convened at 6 monthly intervals to consider and advise on research questions, conduct and the actions that should follow its findings, feeding back to the research team. Recognising patients and the public as key stakeholders in the research, the dissemination plan includes webinars, presentations and reports for patients and patient organisations. We will involve our PPI and patient representatives to ensure that we engage all relevant organisations and that the style and format of our publications is accessible to these audiences.

11 FUNDING

The study funding has been reviewed by the KCH R&I Office and deemed sufficient to cover the requirements of the study.

The research costs for the study have been supported by The National Institute for Health and Care Research (NIHR 132969), confirmed 4th April 2022 for £1.163,742.27.

Breakdown of funding as awarded is detailed in Appendix 3.

King's College Hospital MHS

NHS Foundation Trust

12 DATA HANDLING AND MANAGEMENT

Details of case ascertainment and outline data flows are shown in section 8 and appendix 2 respectively. The research team analysing the data will only have access to de-identified data. Personal data will only be used for data linkage carried out by trusted third parties. Application will be made to the Confidentiality Advisory Group (CAG) for processing of the data without consent under Section 251 of the Health and Social Care Act 2001.

The de-identified clinical data will be stored on a secure server at LSHTM. The secure server will ensure appropriate levels of IT security and complies with the IG toolkit. Only the researchers required to carry out data analysis at LSHTM will have access to the linked data on the secure server. These researchers will have accredited researcher status, have undergone information governance training, and will comply with GDPR.

After the study has ended the data will be retained on the secure data server at LSHTM. Access to the data will be strictly controlled by the Principal Investigator of the study ([name], KCH) and by the co-Principal Investigator ([name], LSHTM). Access will only be given to members of the research team whose role includes data analysis. The Principal Investigator and the co-Principal Investigator will regularly monitor the audit logs they are sent.

The co-Principal Investigator will have control of and act as custodian for the final data generated by the study. In this study, the following parties are involved as data controllers and processors:

Organisation Name	Role	Function	Contact
NHS Digital	Controller	 Creation of data group Creation of Pseudonym Code Provider of Pseudonym Code and NHS Number to NHS BT and ICNARC 	DPO Name [name] ([contact])
NHS Blood and Transplant	Controller	 Provision of data based on NHS D List and sender of details to 	DPO Name [name] ([contact])
ICNARC	Controller	 Provision of data based on NHS D List and sender of details to 	DPO Name [name] ([contact])
Kings College Hospital	Controller	 Oversight of Research Study 	 1.Pl Name [name] ([contact]) 2. [name], Data Protection Officer ([contact])
London School of Hygiene and Tropical Medicine	Processor	 Recipient of data from NHS 	DPO Name [name] ([contact])

King's College Hospital **NHS Foundation Trust**

	D, NHS BT, and ICNARC 2. 2. Complete analytic actions as directed by KCH	
--	---	--

13 MATERIAL/SAMPLE STORAGE

Not applicable: study working with existing routine data only.

